6.5 Other Populations Defined for Tables and Listings

For the purposes of tables and listings a further two populations are utilized:

-
- All screened subjects (for use of subject disposition only)
 - Randomised population (all randomised subjects)

6.6 Protocol Deviations/Violations and Exclusions from Analysis Sets

All violations and exclusions of subjects from analysis populations will be identified and documented at the Classification Meeting prior to study unblinding. The review of each subject's data will be conducted using (but not limited to) the following sources of information:

- Supportive subject listings, provided by the ICON ahead of the Classification Meeting, based on data recorded on the eCRF.
- Protocol Deviation Logs, retrieved from Clinical Trial Management System (CTMS).

7 STATISTICAL CONSIDERATIONS AND ANALYSIS

7.1 Derived Variables

7.1.1 General Variables

Study Day

Study day will be relative to the date of first study medication (Study Day 1) and calculated as:

- (assessment date – date of first dose of study medication) + 1, for assessments on or after the date of first dose of study medication date
- (assessment date – date of first dose of study medication), for assessments prior to date of first dose of study medication

Follow-up time

Follow-up time (days) will be calculated as:

(date of last contact - date of first dose of study medication) + 1

7.1.2 Definitions relative to demographic and other baseline characteristics

Age

Age at informed consent will be calculated as:

Age (years) = (date of informed consent - date of birth + 1) / 365.25

Weight, height and BMI

Weight, recorded in pounds on the eCRF, will be converted in kilograms (1 pound = 0.45359 kg).

Height, recorded in inches on the eCRF, will be converted in centimeters (1 inch = 2.54 cm) (International System of Units).

Body mass index (BMI) will be calculated in kg/m^2 as: $\text{weight (kg)} / (\text{height (m)})^2$.

Temperature

Temperature, recorded in Fahrenheit degrees on the eCRF, will be converted in Celsius degrees:

Celsius degrees = (Fahrenheit degrees - 32) x (5/9)

HH disease duration

Duration of HH disease will be calculated in years as:

(date of informed consent – date of initial diagnosis of HH + 1) / 365.25

7.1.3 Definitions relative to efficacy criteria

7.1.3.1 Total Testosterone

Testosterone Normalisation

A subject is deemed to have achieved testosterone normalisation if their total testosterone value is between 300-1000 ng/dL (10.4-35 nmol/L) inclusive.

To allow for a potential 10-25% decrease in total testosterone that can occur due to diurnal variation in the afternoons (given current testing is restricted to mornings), a stricter secondary definition of normalisation will be used. A subject is deemed to have achieved the secondary definition of testosterone normalisation if their total testosterone value is between 350-1170 ng/dL (12.15-40.6 nmol/L) inclusive. The secondary definition boundaries were derived by averaging the testosterone value that a 25% decrease in would result in the primary definition boundary with the primary definition boundary itself.

Testosterone Overshoot

A subject is deemed to have testosterone overshoot if their total testosterone value is greater than 1000 ng/dL (35 nmol/L).

Time to first Testosterone Normalisation

Time to first Testosterone Normalisation is defined as the time (in days) from the date of first dose of study medication until the date of the first occurrence of testosterone normalisation during the treatment period.

Subjects who do not achieve testosterone normalisation will be censored at their final testosterone assessment during the treatment period (Up to Visit 8).

End of Treatment Testosterone

End of treatment testosterone is defined as the Week 24 total testosterone assessment for subjects that completed the treatment period. For subjects that discontinued the treatment period early, the last on-treatment testosterone assessment will be used as their end of treatment testosterone value.

7.1.3.2 Body Composition

Gynecomastia

The size of glandular breast tissue, recorded in inches on the eCRF, will be converted in centimeters (1 inch = 2.54 cm).

7.1.3.3 International Index of Erectile Function (IIEF)

The IIEF is a 15-item self-administered questionnaire with each question being scored between 0-5 (see Appendix A for scoring conversion). Five sexual function domains will be derived by summing the scores of the associated questions (noted in parentheses below):

1. Erectile function (1,2,3,4,5,15)
2. Orgasmic Function (9,10)
3. Sexual Desire (11,12)
4. Intercourse Satisfaction (6,7,8)
5. Overall Satisfaction (13,14)

If at least one of the questions within a domain is missing then the domain will not be calculated. A higher score denotes a higher level of satisfaction/function

In addition the erectile function domain scores will be classified into the below severity categories:

- No Dysfunction (25-30)
- Mild (22-24)
- Moderate (11-21)
- Severe (1-10)

The minimal meaningful difference in the change from baseline in the erectile function domain score is defined as a change in 2 points for subjects who are mild at baseline, 5 points for subjects who are moderate at baseline and 7 points for subjects who are severe at baseline.

7.1.3.4 Patient-Reported Outcomes Measurement Information System(®) Sexual Function and Satisfaction (PROMIS(®) SexFS)

The PROMIS SexFS PRO measure will be utilized by collecting a 10 item self-administered questionnaire compiled from relevant items in the PROMIS Sexual Function and Satisfaction domains (Flynn et al., 2013). Each question is scored between 0 and 5 (See Appendix B for scoring conversion) and three sexual function domains will be derived by summing the scores of the associated questions (noted in parentheses below) and converting to a standardised T-score (standardised to a scale with mean 50 and Standard Deviation 10 – See Appendix B for conversion tables):

1. Interest in Sexual Activity (1,2)
2. Erectile Function (3)
3. Satisfaction with Sex Life (4,5,6,7,8)

If at least one of the questions within a domain is missing then the domain will not be calculated. In addition if a subject answers any question within a domain with a score of 0 (indicating the subject has not had the item in question) then the domain will also not be calculated.

Questions 9 and 10 (Interfering Factors) will be summarized by raw score as no calibration is available for interfering factors.

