Appendix II: Symptoms and Signs Suggestive of Androgen Deficiency

The following list is symptoms and signs that are suggestive of androgen deficiency:

- Reduced sexual desire (libido) and sexual activity
- Decreased spontaneous erections
- Reduced intensity of orgasm
- Gynecomastia
- Loss of body (axillary and pubic) hair (can be measured by reduced shaving)frequency
- Very small (especially ≤ 5 ml) or shrinking testes
- Infertility or documented oligospermia or azoospermia
- Hot flushes
- Decreased energy, motivation, initiative, and self-confidence
- Feeling depressed
- Mood swings
- Poor concentration and memory
- Sleep disturbance, increased sleepiness
- Mild anemia (normochromic, normocytic, in the female range)
- Reduced muscle bulk and strength
- Increased body fat, body mass index
- Diminished physical or work performance

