8.6.4.5 Change in PRO measures

For some PRO Measures (PROMIS SexFS, PROMIS Fatigue Short Form and PGI-S), not all protocol versions mandated their collection. Subjects originally enrolled using protocol versions 2.0 were not required to collect these measures. To handle such cases, denominators used for analysis will only include the subjects mandated to collect the particular PRO.

IIEF

Descriptive summary tables will be presented for each of the 5 sexual function domain scores (Erectile function, Orgasmic function, Sexual desire, Intercourse satisfaction and Overall satisfaction) and change from baseline scores by treatment regimen and visit.

The change from baseline in each sexual function domain score to Week 24 will be analysed via MMRM in the same manner as the change from baseline in total testosterone (see Section 8.6.3.1), however 90% confidence intervals (instead of 95%) will be presented for all inferences.

The number and proportion of subjects achieving a minimal meaningful difference in the change in IIEF erectile function domain score will be summarised by treatment regimen at each visit and overall.

In addition the change from baseline in the IIEF domains will also be summarised and analysed as described above by erectile function baseline severity (No dysfunction, mild, moderate and severe), baseline total testosterone (<200ng/dL vs \geq 200ng/dL) as assessed by ICON central labs and end of treatment total testosterone (<300ng/dL, 300-500 ng/dL and >500ng/dL) as assessed by ICON central labs.

PROMIS SexFS

Descriptive summary tables will be presented for each of the 3 sexual function domains scores (Interest in Sexual Activity, Erectile Function, Satisfaction with Sex Life), 2 interfering factors raw

scores and change from baseline scores (domain and interfering factor raw scores) by treatment regimen and visit.

The change from baseline in each sexual function domain score and 2 interfering factor raw scores to Week 24 will be analysed via MMRM in the same manner as the change from baseline in IIEF domain scores including subgroup analysis by baseline total testosterone (<200ng/dL vs \geq 200ng/dL) and end of treatment total testosterone (<300ng/dL, 300-500 ng/dL and >500ng/dL) as assessed by ICON central labs.

PROMIS Fatigue Short Form

A descriptive summary table will be presented for the PROMIS Fatigue Short Form standardised T-Score and change from baseline score by treatment regimen and visit.

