8.8.4.2 IIEF Erectile Function Domain Testing

End of treatment testosterone levels (<300ng/dL vs 300-500 ng/dL vs >500 ng/dL) will be tested

against IIEF erectile function domain response of achieving a minimal meaningful difference at Week 24 by a logistic regression model. The end of treatment testosterone factor effect p-value as well as the odds ratio and 95% CI of the pairwise comparison of each end of treatment testosterone level group will be presented.

This process will be repeated to test the association of baseline testosterone level (<200 ng/dL vs >200 ng/dL) against IIEF erectile function domain response of achieving a minimal meaningful difference.

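### The IIEF erectile function responder has no threshold and no stated handling for men without dysfunction at baseline, and the logistic model built on it has no baseline term

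*SAP*

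**What the plan says.** SAP 7.1.3.3 classifies the IIEF erectile function domain score as no dysfunction (25-30), mild (22-24), moderate (11-21) or severe (1-10). The rule for a minimal meaningful difference reads "defined as a change in 2 points for subjects who are mild at baseline, 5 points for subjects who are moderate at baseline". For the remaining dysfunction category the figure given is "7 points for subjects who are severe at baseline". Nothing is given for 25-30. The same section says of the scale: "A higher score denotes a higher level of satisfaction/function".

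The responder is used in two places.

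- **SAP 8.6.4.5:** "The number and proportion of subjects achieving a minimal meaningful difference in the change in IIEF erectile function domain score will be summarised", by regimen, at each visit and overall. Under 8.6.4 the population is ITT.
- **SAP 8.8.4.2:** end-of-treatment testosterone in three groups (below 300, 300-500, above 500 ng/dL) is tested "against IIEF erectile function domain response of achieving a minimal meaningful difference at Week 24 by a logistic regression model". The model is repeated with baseline testosterone split at 200 ng/dL. Under 8.8.4 the population is PP. Testosterone group is the only factor named.

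Men scoring 25-30 can be enrolled. Inclusion criterion 6 (Protocol 9.3.1) asks for at least two symptoms, one of them sexual, and sets no IIEF score. The symptom list in Protocol Appendix II includes "Reduced sexual desire (libido) and sexual activity". SAP 8.6.4.5 itself names no dysfunction as a baseline subgroup for the IIEF domain changes.

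**The concern.** For a man at 25-30 the outcome is undefined. Two programmers could follow this text and differ: one drops him, one counts him as a failure, and a third borrows the mild threshold. Each choice gives a different denominator, and with nothing in the SAP the choice could be made after unblinding. This is the only responder measure of erectile function in the plan.

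The logistic models are more exposed than the responder table. In the table the groups are randomised, so the share of men at 25-30 should be similar across regimens. In 8.8.4.2 the groups are formed by testosterone level, so their mix of baseline severity may differ. Baseline severity also fixes how large a change counts as response (none stated, 2, 5 or 7 points), yet the model has no term for it.

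**Working it through.** The documents give no figure for this analysis, so there is none to reproduce. They also give no expected share of men at 25-30 and no responder rates. Those values below are assumptions.

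**1. Is it the scale ceiling or the missing threshold?** Under SAP Appendix A, items 1-5 score 0-5 and item 15 scores 1-5. The domain minimum is 5 × 0 + 1 = 1 and the maximum is 6 × 5 = 30. A man at 25 can gain 5 points and a man at 28 can gain 2. The ceiling alone does not rule out response across the category; the missing threshold does.

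**2. Does the SAP restrict denominators elsewhere?** Yes. 8.6.4.9 leaves men already normal at baseline out of the time-to-normal analysis. 8.6.4.2 summarises breast tissue size only in men with gynecomastia. 8.6.4.5 limits PRO denominators to men whose protocol version required that PRO. None of these rules covers men at 25-30.

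**3. Responder table, if these men are counted as non-responders.** Let p be the response rate among men with dysfunction and s the share at 25-30, equal across regimens. The reported rate is p(1 − s), so the difference also scales by (1 − s). Assume p = 30% and 50%, with 67 per group (SAP 5) and a two-sided 5% test (SAP 8.1.4). Power is by normal approximation.

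| s | Rates, men kept as failures | Difference (points) | Odds ratio | Power, kept | Power, excluded |
|---|---|---|---|---|---|
| 0% | 30% / 50% | 20 | 2.33 | 66% | 66% |
| 10% | 27% / 45% | 18 | 2.21 | 59% | 61% |
| 20% | 24% / 40% | 16 | 2.11 | 51% | 56% |
| 30% | 21% / 35% | 14 | 2.03 | 44% | 51% |
| 40% | 18% / 30% | 12 | 1.95 | 37% | 45% |

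If the men are excluded, the difference stays at 20 points and the odds ratio at 2.33; only n falls. The risk ratio does not change either way (50/30 = 40/24 = 1.67).

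**4. Logistic model, if these men are counted as non-responders.** Assume the same 40% response among men with dysfunction in two testosterone groups, so the true odds ratio is 1.

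- Shares at 25-30 of 10% and 30%: rates are 0.40 × 0.90 = 0.36 and 0.40 × 0.70 = 0.28. Odds ratio = (0.28/0.72) / (0.36/0.64) = 0.69.
- Shares reversed: (0.36/0.64) / (0.28/0.72) = 1.45.
- Equal shares of 20%: both rates are 0.32 and the odds ratio is 1.00.

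**5. Sister model.** SAP 8.8.4.1 tests the PROMIS sexual function domains against the same testosterone groupings and includes the baseline value and its interaction with visit. SAP 8.8.4.2 has no counterpart.

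**6. Direction (a wording point).** The threshold carries neither a sign nor an at-least operator, whereas 8.7.3 writes the operator for blood pressure changes. For a moderate man (threshold 5), with an assumed SD of change of 7 and mean change 0, improvement only gives 1 − Φ(5/7) = 24%; a literal either-direction count gives 48%. At mean change 4 the figures are 44% and 54%.

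**The case against.** The best defence is that the SAP never says men at 25-30 are failures. It ties the threshold to mild, moderate and severe men, so for the others the outcome is undefined, which is not the same as not achieved. SAP 7.2.1 makes observed cases the default and describes non-responder imputation only for the primary endpoint. Excluding these men is a natural reading, and then nothing is diluted. This stands as far as it goes: a reader might infer that the responder results are diluted as planned, and the documents do not support that. They leave the matter open.

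A reader might also infer that men who worsen will be counted as responders. The documents point the other way: higher is better, the analyses speak of achieving the difference and of response, and the stated objective is improvement in erectile function. This is a clarification only.

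A third tempting inference is that the 8.8.4.2 odds ratios are pushed toward or past the null. No passage shows how baseline erectile function varies with testosterone among men who all had two screening values below 300 ng/dL. The bias can go either way and vanishes when shares are equal.

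Finally, the continuous IIEF domain changes are analysed by MMRM with baseline adjustment (8.6.1) and repeated by baseline severity, including no dysfunction (8.6.4.5). That is real mitigation for the question of benefit, but it does not define the responder or adjust the logistic models.

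**Conclusion.** The gap is real: one of four baseline categories, which the SAP itself expects to be populated, has no threshold, and neither analysis says how it is handled. The consequences are conditional. If men at 25-30 are counted as non-responders, proportions and differences shrink by their share (20 to 16 points at an assumed 20%), and the 8.8.4.2 odds ratios can be biased in either direction if baseline severity differs between testosterone groups (0.69 or 1.45 in the example, where the truth is 1). If the men are excluded, the table is not diluted and that source of bias goes, but the model still ignores the variable that sets the threshold. The actual size cannot be computed from the documents.

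The impact is confined to an exploratory endpoint and an association analysis. The primary endpoint and sample size are untouched.

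**What to change.** Before unblinding, amend the SAP as follows.

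- **8.6.4.5 and 8.8.4.2:** restrict the responder table and both logistic models (end-of-treatment and baseline testosterone), numerator and denominator, to men with a baseline erectile function score below 25. Show men at 25-30 separately, for example as a count and their score change by regimen.
- **8.8.4.2:** add baseline severity category (mild, moderate, severe) as a factor. This does not make the testosterone groups comparable in other respects, but it removes the imbalance tied directly to the response definition.
- **7.1.3.3, as a clarification:** define response as an increase from baseline of at least 2, 5 or 7 points for mild, moderate and severe men.

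The severity category is already derived, so the change is wording and a little programming. The price is smaller denominators and two more parameters in each logistic model. In the step 3 example, restriction does not cost power compared with keeping these men as failures (56% against 51% at a 20% share).

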7.1.3.5 PROMIS(®) Fatigue Short Form

The PROMIS Fatigue Short Form measure is an 8-item self-administered questionnaire assessing the extent of fatigue and its impact on work and functioning in the last 7 days. Each question is scored between 1 and 5 (See Appendix C for scoring conversion) and a total raw score will be calculated by summing the values of the response to each question. A standardised T-Score will then be calculated by standardizing the raw total score to a scale with mean 50 and SD 10 (See Appendix C for conversion tables).

If between 1 and 4 items (inclusive) have a missing response then the raw total score will be

estimated from the non-missing responses using the below formula:

$$\text{Total Raw Score} = \frac{\text{Sum of scores of items answered} \times 8}{\text{Number of items answered}}$$

If the result is a fraction, round up to the nearest whole number. If greater than 4 items have a missing response then the total raw score will not be calculated

7.1.3.6 Brief Fatigue Inventory (BFI)

The BFI is an 9-item self-administered questionnaire, providing an assessment of the severity of fatigue and its impact on the subject’s ability to function at present and in the previous 24 hours. A global fatigue score is calculated by deriving the mean score of each of the non-missing questions.

If more than 4 questions have a missing response, then the global fatigue score will not be calculated

7.1.3.7 36-Item Short Form Health Survey (SF-36)

The SF-36 questionnaire is a multidimensional instrument that evaluates quality of life. It measures 8 general health concepts or domains: Vitality, Physical Functioning, Bodily Pain, General Health Perceptions, Physical Role Functioning, Emotional Role Functioning, Social Role Functioning and Mental Health. These domains will also be summarised as physical and mental component scores. Please see Appendix D for detailed scoring of each domain and component scores.

7.1.3.8 Patient Global Impression of Status items (PGI-S)

Three patient global impression items will be included to assess the patients’ overall impression of their current health status and thus to evaluate the performance of the other PROs in this patient population. Each response will be converted to a numeric score for summarising using the below conversions:

Response	Score
Not at all	1
A little bit	2
Somewhat	3
Quite a bit	4
Very much	5

7.1.3.9 Actigraphy Derived Activity and Sleep Parameters

The Autograph Link is a portable device that measures gross motor movements featuring a validated 3-axis accelerometer and data filtering technology that captures and records continuous, high resolution physical activity and sleep/wake information.

Subjects are instructed to wear the monitor for 7 days consecutively starting with the day of the scheduled Visit 1, and 5 and 7 days consecutively before Visits 8 and 11. Only data collected during the specified visit windows (See Appendix E) on days were the device had been worn for ≥ 1152 minutes (i.e 80% daily compliance) and deemed (either algorithmically or hardware detected by the device) to have been collected while the device was being worn will be used. All evaluable data within the specified visit window will be used to derive each parameter at each visit. However if there are less than 3 evaluable days' worth of data collected within the window the parameter will be set to missing.

Activity Parameters

The average number of minutes spent per day within each activity category below will be calculated for each visit:

- Sedentary
- Light
- Lifestyle
- Moderate
- Vigorous
- Very Vigorous
- MVPA (Moderate to Very Vigorous Physical Activity)

In addition the average daily total number of steps and total activity counts (across all 3 axis) will be calculated as well as the maximum daily total activity count across each visit.

Sleep Parameters

The average length of awakenings (minutes), number of awakenings, number of minutes asleep (minutes), number of minutes awake (minutes) and proportion of time spent asleep during the sleep period will be calculated per day for each scheduled visit. Sleep periods starting before 5am will be assigned to the previous day.

7.1.3.10 Grip Strength

Grip strength assessment using a hand held dynamometer will be used as a surrogate measure of muscle strength. During this assessment, the subject will squeeze the device three times with each hand. An average (mean) of three measurements for each hand will be calculated at each visit.

7.1.3.11 Semen Parameters

Semen concentration will be assigned into the below categories:

- Normal (>15 million sperm/mL)

- Oligospermia: Mild (10-15 million sperm/mL)
- Oligospermia: Moderate (5-10 million sperm/mL)
- Oligospermia: Severe (<5 million sperm/mL)
- Azoospermia (complete absence of sperm)

In addition total motile count will be derived by the below formula:

Total Motile Count = Volume of Semen x Semen Concentration x percentage motile

